4 OBJECTIVES OF THE STUDY

Primary Objective

To compare the treatment effect of Circadin[®] 2/5 mg to that of placebo on sleep maintenance (TST) as assessed by the Sleep and Nap Diary ([Appendix 1](#)) after 13 weeks of double-blind treatment.

Secondary Objectives

- To compare the treatment effect of Circadin[®] 2/5 mg to that of placebo on sleep latency as derived from a Sleep and Nap Diary ([Appendix 1](#)) after 13 weeks of double-blind treatment
- To compare the treatment effect of Circadin[®] 2/5 mg to that of placebo on the duration of wake after sleep onset period as derived from a Sleep and Nap Diary after 13 weeks of double-blind treatment
- To compare the treatment effect of Circadin[®] 2/5 mg to that of placebo on number of awakenings as derived from a Sleep and Nap Diary after 13 weeks of double-blind treatment
- To compare the treatment effect of Circadin[®] 2/5 mg to that of placebo on the duration of the longest sleep period as derived from a Sleep and Nap Diary after 13 weeks of double-blind treatment
- To assess the treatment effect of Circadin[®] 2/5 mg to that of placebo on children's social functioning at home, in school, and community settings as assessed by the Children Global Assessment Scale (CGAS; [Appendix 3](#)) after 13 weeks of double-blind treatment
- To compare the treatment effect of Circadin[®] 2/5 mg to that of placebo on children's behavior at home and in school as assessed by the Strength and Difficulties Questionnaire (SDQ; [Appendix 4](#)) after 13 weeks of double-blind treatment
- To compare the number of dropouts between Circadin[®] 2/5 mg to that of placebo during the 13 weeks of double-blind treatment
- To compare the treatment effect of Circadin[®] 2/5 mg to that of placebo on sleep parameters as measured by actigraphy after 13 weeks of double-blind treatment
- To compare the safety and tolerability of Circadin[®] treatment to that of placebo and evaluate the safety and tolerability throughout the study including the run-out (withdrawal) period using AE eliciting method Treatment Emergent Signs and Symptoms questionnaire (TESS; [Appendix 5](#))
- To assess vital signs and physical examinations in Circadin[®] and placebo groups

Exploratory Objectives

- To evaluate the effect of Circadin[®] 2/5 mg on all sleep variables derived from the Sleep and Nap Diary after 3 weeks of double-blind treatment (Week 15), and after 13, 26, and 39 weeks of open-label treatment (Weeks 28, 41, and 54) as compared to baseline (Week 2)

- To compare the treatment effect of Circadin[®] 2/5 mg to that of placebo on sleep disturbance as assessed by Composite Sleep Disturbance Index (CSDI; [Appendix 6](#)) score after 3 and 13 weeks of double-blind treatment (Weeks 5 and 15), after 13, 26, 39, and 91 weeks of open-label treatment (Weeks 28, 41, 54, and 106, respectively), and at the end of study visit (Week 108) as compared to baseline (Week 2)
- To assess the treatment effect of Circadin[®] 2/5 mg on children's social functioning at home, in school, and community settings as assessed by the CGAS ([Appendix 3](#)) after 13 weeks (Week 28) of Circadin[®] open-label treatment as compared to baseline (Week 2)
- To assess the treatment effect of Circadin[®] 2/5 mg on children's behavior at home and in school as assessed by the SDQ ([Appendix 4](#)) after 13 weeks (Week 28) of Circadin[®] open-label treatment as compared to baseline (Week 2)
- To assess the level of caregiver's daytime sleepiness (i.e., NOT the child's sleepiness) during the study using the Epworth Sleepiness Scale (ESS; [Appendix 7](#)) at Weeks 0, 2, 5, 15, 28, 41, 54, 106, and 108
- To assess the level of caregiver's quality of sleep (i.e., NOT the child's quality of sleep) at night during the study using the Pittsburgh Sleep Quality Index (PSQI; [Appendix 8](#)) at Weeks 0, 2, 5, 15, 28, 41, 54, 106, and 108
- To assess the level of caregiver's well-being (i.e., NOT the child's well-being) during the study using the World Health Organization Well-Being Index (WHO-5) questionnaire ([Appendix 9](#)) at Weeks 0, 2, 5, 15, 28, 41, 54, 106, and 108
- To compare the treatment effect of Circadin[®] 2/5 mg to that of placebo on children's body mass index (BMI) and Z-score after 3 and 13 weeks of double-blind treatment, and to evaluate the effect of Circadin[®] 2/5/10 mg compared to baseline, at the end of the open-label period, and at the end of the placebo run-out period
- To assess the treatment effect of Circadin[®] 2/5/10 mg on pubertal status the Tanner scale will be used in children ≥ 8 years of age. For children ≤ 5 years of age, only height and head circumference will be used to stage children development. Between the age of 5 and 8 the children's physical development will be determined using the BMI (baseline through Week 108)
- In children diagnosed with epilepsy, to compare the effect of Circadin[®] 2/5 mg to that of placebo on the number and severity of epilepsy seizures during double-blind treatment and to assess the effect of Circadin[®] 2/5/10 mg during the open-label period using seizure diaries

5 INVESTIGATIONAL PLAN

5.1 OVERALL STUDY DESIGN

This is a randomized placebo-controlled study in children diagnosed with ASDs and neurodevelopmental disabilities caused by neurogenetic diseases. Children will have a documented history of these disorders, as confirmed or consistent with the International Classification of Diseases (ICD-10) or Diagnostic and Statistical Manual of Mental Disorders, Fifth Edition, Text Revision (DSM-5/4) criteria, having International Classification of Sleep Disorders (ICSD) criteria-based sleep disturbances modified to take into account the uniqueness of insomnia in the pediatric population at screening.

The children will undergo 4 weeks of basic sleep hygiene and behavioral intervention, which will serve as a wash-out period from any hypnotics; a gradual withdrawal will take place during the first 2 weeks and a complete withdrawal of prohibited medications will take place during the last 2 weeks.

Children who are still found to be eligible for the study after the 4-week, basic sleep hygiene and behavioral intervention wash-out period, will continue in a 2-week SB placebo run-in period. In order to be eligible for the 2-week SB placebo run-in period, the child should not have responded to sleep hygiene and behavioral intervention during the first 4 weeks and therefore will not need to continue this therapy during the study. Children with a documented history of sleep hygiene and behavioral intervention, who are still found eligible, will enter directly into the 2-week SB placebo run-in period.

Children with a documented history of sleep hygiene and behavioral intervention who are taking prohibited medications will not require additional training and will undergo a 2-week wash-out period before Visit 1 (e.g., Weeks -2 through 0 to wash out melatonin or any other prohibited medications). During these 2 weeks there is no need to complete the sleep and nap diary.

After the 4-week sleep hygiene (for children who do not have a documented history of sleep hygiene and behavioral intervention) and 2-week SB placebo run-in period, children who are still found eligible for study participation will be randomized in a 1:1 ratio to receive either Circadin[®] 2 mg or placebo for 3 weeks in a double-blind treatment period. After 3 weeks of treatment, on the last day of Week 5 \pm 3 days (Visit 3), sleep variables will be assessed to determine if dose modification (an increase to 5 mg) is required. Children will then continue on 2 or 5 mg of Circadin[®] or placebo for an additional double-blind period of 10 weeks. This double-blind period will be followed by an open-label period of 13 weeks. At the end of the 13-week open-label period on the last day of Week 28 \pm 3 days (Visit 5), sleep variables will be assessed to determine if a potential additional dose modification (i.e., an increase either to 5 mg for patients who are still on 2 mg or an increase to 10 mg for patients who are on 5 mg) is necessary. Children will continue at 2, 5, or 10 mg Circadin[®] in an open-label period for another 78 weeks of follow-up, which will include continuous safety monitoring and 2 efficacy assessment time points at Weeks 41 and 54. The study will end with a 2-week SB placebo run-out period-

Each patient will participate in the study until the end of the second open-label safety follow-up period, and 2-week SB placebo run-out period. Study duration will be 112 weeks, including the 4-week wash-out period with sleep hygiene and behavioral intervention.

Circadin[®] and placebo are to be administered orally, 1 portion of minitablets daily, taken postprandial 0.5 to 1 hour before desired bedtime (bedtime should be defined as age-appropriate bedtime). The minitablets should be swallowed whole and should not be crushed or halved.

The study population will include male and female children 2 to 17.5 years of age with confirmed history of ASDs or neurodevelopmental disabilities caused by neurogenetic diseases. At Visit 1, enough eligible male and female children, of ages 2 to 17.5 years, will be screened for the study to allow for 120 patients to then be randomized in a 1:1 ratio to receive Circadin[®] or placebo at Visit 2. A minimum of 90 children are expected to complete the double-blind and first open-label period. A minimum of 50 children are expected to complete the second open-label safety follow-up period.

5.2 EFFICACY ASSESSMENTS

Primary Efficacy Endpoint

The primary efficacy parameter is TST time as assessed by a Sleep and Nap Diary after the 13-week, double-blind treatment period.

Secondary Efficacy Endpoints

- Sleep latency as assessed by a Sleep and Nap Diary after 13 weeks (Week 15) of double-blind treatment
- Duration of wake after sleep onset period from the Sleep and Nap Diary after 13 weeks (Week 15) of double-blind treatment
- Number of awakenings from the Sleep and Nap Diary after 13 weeks (Week 15) of double-blind treatment
- Longest sleep period from the Sleep and Nap Diary after 13 weeks (Week 15) of double-blind treatment
- Social functioning at home, in school, and in community settings as assessed by the CGAS after 13 weeks (Week 15) of double-blind treatment
- Behavior at home and in school as assessed by the SDQ after 13 weeks (Week 15) of double-blind treatment
- Number of dropouts during the 13-week (Week 15) double-blind treatment period
- Assessment of sleep parameters by actigraphy after 13 weeks (Week 15) of double-blind treatment

Exploratory Efficacy Endpoints

- Sleep variables as assessed by the Sleep and Nap Diary at baseline (Week 2), after 3 weeks of double-blind treatment (Week 5), and after 13, 26, and 39 weeks of open-label treatment (Weeks 28, 41, and 54)
- Sleep disturbance as assessed by the CSDI score at baseline after 3 and 13 weeks of double-blind treatment (Weeks 5 and 15, respectively), after 13, 26, 39, and 91 weeks of open-label treatment (Weeks 28, 41, 54, and 106, respectively), and at the end of study visit (Week 108)
- Social functioning at home, in school, and in community settings as assessed by the CGAS after 13 weeks (Week 28) of open-label treatment
- Behavior at home and in school as assessed by the SDQ after 13 weeks (Week 28) of open-label treatment
- Caregiver's daytime sleepiness (i.e., NOT the child's sleepiness) during the study as assessed by the ESS (Weeks 0, 2, 5, 15, 28, 41, 54, 106, and 108)
- Caregiver's well-being (i.e., NOT the child's well-being) during the study as assessed by the WHO-5 questionnaire (Weeks 0, 2, 5, 15, 28, 41, 54, 106, and 108)
- Caregiver's quality of sleep (i.e., NOT the child's quality of sleep) at night during the study as assessed by the PSQI questionnaire (Weeks 0, 2, 5, 15, 28, 41, 54, 106, and 108)

5.3 SAFETY ASSESSMENTS

Safety Endpoints (Secondary)

- Assessment of AEs throughout the study after Visit 1 and upon study withdrawal using the TESS
- Vital signs at each visit including the placebo run-out (withdrawal) period
- Physical examination at each visit including the placebo run-out (withdrawal) period

Safety Endpoints (Exploratory)

- BMI and Z-score assessed during the study
- Pubertal assessment using the Tanner scale during the study (The Tanner scale will be used to assess and stage physical development in children ≥ 8 years of age. For children ≤ 5 years of age, only height and head circumference will be used to stage children development. Between the age of 5 and 8, the children's physical development will be determined using BMI.
- In children diagnosed with epilepsy, the number and severity of epilepsy seizures assessed during the study using Epilepsy Seizures Diaries.

Table 5-1: Study Treatment Schedule

Period	Wash-out Sleep Hygiene	Run-in, Single-blind		Double-blind				Open-Label							Run-out, Single-Blind			
Treatment	No drug intervention ¹	Placebo		Circadin® 2 mg or PBO		Circadin® 2 mg, 5 mg, or PBO		Circadin® 2 mg or 5 mg		Circadin® 2 mg, 5 mg, or 10 mg							Placebo	
Week	-4 to 0	1	2	3	5	6	15	16	28	29	41	42	54	55	106	107	108	
Visit³	SCRN first day of Week -4, ±3 days	Visit 1 first day of Week 1, ±3 days	Visit 2 last day of Week 2, ±3 days randomization/baseline visit		Visit 3² last day of Week 5, ±3 days dose modification		Visit 4 last day of Week 15, ±3 days		Visit 5² last day of Week 28, ±3 days dose modification		Visit 6 last day of Week 41, ±7 days		Visit 7 last day of Week 54, ±7 days		Visit 8 last day of Week 106, ±7 days		End of Study last day of Week 108, ±3 days	

SCRN = Screening; PBO = placebo

* The visit should be carried out within ±3 days.

** The visit should be carried out within ±7 days.

¹ First 2 weeks are a gradual withdrawal and the last 2 weeks are a complete withdrawal of prohibited medications.

² Data analysis (assessment of sleep variables) will be performed at the end of Week 5 (Visit 3) and Week 28 (Visit 5) to determine if a dose modification (i.e., an increase to 5 mg or 5/10 mg Circadin®, respectively) is required.

³ All visits, except screening and Visit 1 will occur on the last day of the week in which they occur, as indicated above.

Table 5-2: Schedule of Study Assessments

	Wash-out Sleep Hygiene		Run-in, Single-blind	Double-blind		Open-label				Run-out, Single-Blind
	Screening -4 Weeks*	Visit 1/ Week 0*	Visit 2 /Randomization/ Baseline Visit* Week 2	Visit 3/ Week 5*	Visit 4/ Week 15*	Visit 5/ Week 28 ¹ *	Visit 6/ Week 41**	Visit 7/ Week 54**	Visit 8/ Week 106**	End of Study Visit/ Week 108*
Screening procedures										
Explanation of Study	X									
Informed consent	X									
Eligibility	X	X	X							
Medical history	X	X								
Demographic data	X									
Sleep problem verification	X	X	X							
Inclusion/ Exclusion	X									
Sleep hygiene training booklet	X									
Randomization			X							
Dose Modification				X		X				
Safety Assessments										
Compliance verification			X	X	X	X	X	X	X	X
Vital signs	X	X	X	X	X	X	X	X	X	X
Physical examination	X	X	X	X	X	X	X	X	X	X
Body weight and height for BMI and Z-score	X	X	X	X	X	X	X	X	X	X
Adverse events			X	X	X	X	X	X	X	X
Pregnancy test ²	X		X		X					X

	Wash-out Sleep Hygiene		Run-in, Single-blind	Double-blind		Open-label				Run-out, Single-Blind
	Screening -4 Weeks*	Visit 1/ Week 0*	Visit 2 /Randomization/ Baseline Visit* Week 2	Visit 3/ Week 5*	Visit 4/ Week 15*	Visit 5/ Week 28 ^{1*}	Visit 6/ Week 41**	Visit 7/ Week 54**	Visit 8/ Week 106**	End of Study Visit/ Week 108*
Pubertal Assessment (Tanner) and Physical Development ³			X		X	X			X	X
Epilepsy Diary ⁴	X	X	X	X	X	X	X	X	X	X
TESS ⁵		X	X	X	X	X	X	X	X	X
Efficacy Assessments										
Sleep and Nap Diary ⁶	X	X	X	X	X	X	X	X		
CSDI ⁷		X	X	X	X	X	X	X	X	X
Actigraphy ⁸		X	X ⁸	X	X ⁸					
CGAS ⁵		X	X	X	X	X				
SDQ ⁷		X	X	X	X	X				
ESS ⁷		X	X	X	X	X	X	X	X	X
PSQI ⁷		X	X	X	X	X	X	X	X	X
WHO-5 ⁷		X	X	X	X	X	X	X	X	X
IMP Dispensing		X	X	X	X	X	X	X ⁹	X	

Footnotes for [Table 5-2](#):

* The visit should be carried out within ± 3 days.

** The visit should be carried out within ± 7 days.

1. End of Phase I of the study

2. For female patients of childbearing potential, urine dipstick pregnancy tests will be administered.

3. The Tanner scale will be used to assess and stage physical development in children ≥ 8 years of age. For children ≤ 5 years of age, only height and head circumference will be used to stage children development. Between the age of 5 and 8 the children's physical development will be determined using the BMI.

4. For patients with epilepsy and a history of seizures, the Epilepsy Seizures Diary is to be dispensed to the parent at each visit and completed only on the days that the patient has a seizure, which should include the date, time, duration and type of the seizure ([Appendix 10](#)). The Epilepsy Seizures Diary is to be completed only by the patient's parent/caregiver after each seizure and to be entered into the electronic case report form (eCRF) by the site at each study visit.

5. The TESS ([Appendix 5](#)) and CGAS ([Appendix 9](#)) must be administered and completed by the Investigator with the parent/caregiver's input at the study visit indicated.

6. Sleep and Nap Diary is to be completed 14 nights before each scheduled visit ([Appendix 1](#) and [Appendix 2](#)). The parent will complete the questionnaire either directly into the eCRF or on the printed version. If the printed version is used, at a later time point, the site coordinator will enter the questionnaire data into the eCRF. At the screening visit, the Sleep and Nap Diary is dispensed. The study coordinator/Investigator must provide guidance to the parents on how to complete the diary by reviewing the diary question by question and explaining the importance of completing all required data entry every morning, preferably within 2 to 3 hours after the patient wakes up. It is critical that the study coordinator/Investigator provide a thorough review and explanation of the diary to the parents to ensure that the data retrieved is high quality and reliable. A follow-up phone call to remind patients to begin filling out Sleep and Nap Diaries will be made every week before Visits 1 and 2, as well as every week during the study period up to Visit 7. Between Visits 7 and Visit 8, the phone call will be made once a month.

7. CSDI ([Appendix 6](#)), SDQ ([Appendix 8](#)), ESS ([Appendix 7](#)), WHO-5 ([Appendix 9](#)), and PSQI ([Appendix 8](#)) are to be completed by the site coordinators/Investigators with the parents/caregiver, by posing the questions in the questionnaires and filling in the responses given by the parents/caregiver. Note: The ESS, WHO-5, and PSQI are to assess sleepiness, quality of sleep, and well-being of the parent/caregiver's and NOT the child.

8. Actigraphy (Actiwatches) is dispensed to patients at Visit 1 so that they can be worn for 14 days prior to Visit 2. The device is to be delivered to the patient's home no earlier than 3 weeks before Visit 4 to ensure the actigraphy maintains adequate battery strength. Actiwatches are to be worn 14 nights before Visit 2 and Visit 4 and collected at Visit 2 and Visit 4. The actigraphy should be worn by the patient from drug-intake at night until lights on in the morning.

9. The study site can choose to not dispense all investigational medicinal product (IMP) up to Visit 8 at once. The site can send new IMP to patients in quarterly intervals (i.e., in periods of 3 month intervals).

6 STUDY POPULATION AND SELECTION

The study population for this study will include patients with confirmed history of ASDs (pervasive developmental disorders) according to DSM-5/4 criteria or ICD-10 or neurodevelopmental disabilities caused by neurogenetic diseases (SMS, Angelman syndrome, Bourneville's disease [tuberous sclerosis]). Enough patients will be screened for the study to allow for 120 patients to be randomized in a 1:1 ratio to receive Circadin[®] or placebo at Visit 2. Patients will be screened for the study after their legal guardians provide written, informed consent on their behalf (refer to [Section 16.2](#) for further details). In order to be randomized to treatment, patients must meet all inclusion criteria listed in [Section 6.1](#) and none of the exclusion criteria listed in [Section 6.2](#).

6.1 INCLUSION CRITERIA

To be eligible for study entry, all patients must satisfy all of the following criteria at screening:

- Must be children 2 to 17.5 years of age at Visit 2 who comply with taking the study drug.
- Must have written informed consent provided by a legal guardian and assent (if needed).
- Must have a documented history of ASD according to or consistent with the ICD-10 or DSM-5/4 criteria, or neurodevelopmental disabilities caused by neurogenetic diseases (SMS, Angelman syndrome, Bourneville's disease [tuberous sclerosis]) as confirmed by case note review showing that diagnosis was reached through assessment by a community pediatrician or pediatric neurologist or other health care professionals experienced in the diagnosis who took into account early developmental history and school records.
- Must have current sleep problems including: a minimum of 3 months of impaired sleep defined as ≤ 6 hours of continuous sleep AND/OR ≥ 0.5 hour sleep latency from light off in 3 out of 5 nights based on parent reports and patient medical history. (The maintenance and latency problems do not necessarily have to be in the same 3 nights of the week.)
- May be on a stable dose of non-excluded medication for 3 months, including anti-epileptics, anti-depressants (selective serotonin reuptake inhibitors [SSRIs]), stimulants, all mood changing drugs and β -blockers. (Only morning administration of β -blockers is allowed since β -blockers at night have the potential to reduce endogenous melatonin levels and might cause disturbed sleep).
- The sleep disturbance is not due to the direct physiological effects of any concomitant medications such as SSRIs, stimulants, etc.

After completing 4 weeks of sleep hygiene training (for those who need it) and 2 weeks of placebo run-in, patients will be eligible to continue the study if they comply with the following:

- Continue to fulfil sleep problem criteria (see Inclusion Criterion 4) based on the completed Sleep and Nap Diary entered into the electronic case report form (eCRF)

- Parents demonstrate compliance in Sleep and Nap Diary completion (5 out of 7 nights). Compliance means that in at least 5 out of 7 nights per week (total of 2 weeks before each scheduled visit) the parents complete the diary pages with all mandatory questions (mandatory questions are marked with an asterisk [*] in [Appendix 1](#)).
- Continue to fulfil all other eligibility criteria

6.2 EXCLUSION CRITERIA

Children who meet any of the following criteria will be excluded from participating in the study:

- Have had treatment with any form of melatonin within 2 weeks prior to Visit 1
- Have a known allergy to melatonin or lactose
- Have a known moderate to severe sleep apnea
- Have an untreated medical/ineffectively treated/psychological condition that may be the etiology of sleep disturbances
- Did not respond to previous Circadin® therapy based on past medical history records in the last 2 years
- Are taking or have been taking prohibited medication within 2 weeks prior to Visit 1 ([Section 7.1](#))
- Are females of child-bearing potential that are not using contraceptives and/or breastfeeding and that are sexually active (Abstinence is an acceptable method of contraception.)
- Pregnant females
- Are currently participating in a clinical trial or have participated in a clinical trial involving medicinal product within the last 3 months prior to the study (this does not include patients who participated in the Phase I PK study who can be already included in the study).
- Children with known renal or hepatic insufficiency

6.3 WITHDRAWAL OF PATIENTS FROM TREATMENT

Children must be withdrawn from the clinical study if any of the following reasons occur:

- The parents or the patient withdraw their consent.
- The Investigator considers, for safety reasons, it is in the best interests of the patient that the patient be withdrawn from the study.
- A protocol violation or inter-current illnesses occurs, which, in the clinical judgment of the Investigator or after discussion with the Sponsor, may invalidate the study by interfering with the investigational medicinal product (IMP).
- It is discovered that the patient has entered the study in violation of the protocol.
- A significant protocol violation occurs during the study (e.g., a patient violates a major Inclusion/Exclusion criteria; [Section 13.3.2](#)).

- The randomization code is broken for that patient by any 1 of the staff at the clinical study site.
- The patient has taken any prohibited medication listed in [Section 7.1 \(Appendix 11\)](#).
- The patient is lost to follow-up.

The date and reason for withdrawal should be noted in the Withdrawal Form in the eCRF. A parent who withdraws consent will be asked by the Investigator to give a reason, but is not obligated to do so. A patient who withdraws from the clinical study should, if possible, be seen for a Withdrawal Visit scheduled as soon as possible and the end of study procedures should be carried out, as shown in [Section 8.19](#), after the patient has withdrawn from the clinical study. No new information will be collected from the patient except information collected in relation to the scheduled Follow-up Visit or needed for the follow-up of AEs or SAEs.

If a patient is withdrawn from the study, no replacement will be considered.

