7.6 TREATMENT COMPLIANCE

Treatment compliance will be calculated at each study visit by counting returned minitables and using the following formula, except for Visit 8, where treatment compliance will be determined according to the parents reporting on the amount of tablets the child has taken since Visit 7:

$$\text{Compliance (\%)} = \frac{\text{Number of tablets dispensed} - \text{Number of tablets returned}^* - \text{Number of tablets lost}}{\text{Number of minitables per day} \times \text{Number of days since last visit}} \times 100$$

* In case patients/parents forgot to bring in the unused IMP, the number of tablets returned is to be replaced by the number of tablets remaining in the IP pack, as reported by the patient.

Any divergence from the accepted level of compliance (70% to 130% of expected consumption) is to be investigated by the Investigator and could lead to withdrawal of the patient from the study.

Treatment compliance will be recorded in the patient's eCRF by the Investigator.

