13.3.2 Protocol Deviations, Violations, and Exceptions

A protocol deviation is nonadherence to protocol-specific study procedures or schedules that does not involve inclusion/exclusion criteria, primary objective variable criteria, and/or GCP guidelines. Deviations are considered minor and do not impact the study.

A protocol violation is any significant divergence from the protocol, i.e., nonadherence on the part of the patient, the Investigator, or the Sponsor to protocol-specific inclusion/exclusion criteria, primary objective variable criteria, and/or GCP guidelines. Protocol violations will be identified and recorded, by study site personnel, on the eCRF.

In this study, significant protocol violations will be defined as those that affect the assessment of safety or efficacy. The significant protocol violations will be agreed prior to database lock and will be categorised as follows:

- Patient's overall treatment compliance for the study is less than 70% or greater than 130% throughout the study
- Patient fails to meet any inclusion criteria or meets any exclusion criteria
- Any issues related to Sleep and Nap Diary completion
- Patient takes a prohibited medication during the study
- Wrong IMP kit dispensed
- Patient has an insufficient wash-out of prohibited medications prior to beginning the 2-week SB placebo run-in period of the study
- Other, defined as any deviation that causes the Investigator to withdraw the patient from the study for the reason "protocol violation", "protocol deviation" or "protocol non-compliance" on the study completion/withdrawal page of the eCRF

As a matter of policy, the Sponsor will not grant exceptions to protocol-specific entry criteria to allow patients to enter a study. If under extraordinary circumstances such action is considered ethically, medically, and scientifically justified for a particular patient, prior approval from the Sponsor and the responsible Institutional Review Board (IRB)/IEC, in accordance with the SOP, is required before the patient will be allowed to enter the study. If investigative site personnel learn that a patient who did not meet protocol eligibility criteria was entered in a study (a protocol violation), they must immediately inform the Sponsor. Such patients will be discontinued from the study, except in a rare instance following review and written approval by the Sponsor and the responsible IRB/IEC, according to the applicable SOP.

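### Protocol 6.3 read with 13.3.2 requires withdrawal for diary-completion issues that 12.11 leaves to the investigator, and nothing says which rule governs

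*Protocol*

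**What the plan says.** **Protocol 6.3** opens its list with "Children must be withdrawn from the clinical study if any of the following reasons occur". One reason is that "A significant protocol violation occurs during the study"; an eligibility breach is given as an example, with a cross-reference to 13.3.2. After withdrawal, "No new information will be collected from the patient except information collected in relation to the scheduled Follow-up Visit" or for follow-up of adverse events, and "If a patient is withdrawn from the study, no replacement will be considered".

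**Protocol 13.3.2** lists the categories of significant violation. One is "Any issues related to Sleep and Nap Diary completion", with no visit limit and no threshold. It also says that "The significant protocol violations will be agreed prior to database lock". Its only discontinuation order concerns children found to have been ineligible: "Such patients will be discontinued from the study, except in a rare instance".

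**Protocol 12.11** defines diary compliance as mandatory items completed on at least 5 of 7 nights in each of the two weeks before a visit. Failure at any visit is left to the investigator as regards exclusion, except that at Visits 1 and 2 compliance is an entry requirement. Failure at Visits 3 and 5 bars a dose increase, counts as a significant violation under 13.3.2 and is recorded in the eCRF. **Section 7.3.1** keeps the current dose when a dose-increase criterion, diary compliance included, is not met.

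**Protocol 7.6** says that drug compliance outside 70% to 130% "could lead to withdrawal of the patient from the study".

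**SAP 7** removes children with a major deviation up to the end of the double-blind phase from the per-protocol set. Two separate grounds matter here: meeting a withdrawal criterion without being withdrawn, and completing the diary on fewer than 3 of 7 nights per week. **SAP 11.1.1** accepts a post-baseline mean TST from 3 nightly values per week.

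**The concern.** The same event, a poorly kept diary at Visit 3, has two consequences in the Protocol: compulsory withdrawal through 6.3 and 13.3.2, and investigator discretion through 12.11. A site has to decide at the visit and cannot wait for a classification agreed before database lock.

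If the site withdraws the child, diary collection stops ten weeks before the primary endpoint is measured. The child may have been withdrawn over data that the SAP would have accepted. If the site keeps the child, the analysis team has a literal ground for removing the child from the per-protocol set. Either result follows from which clause was read and has nothing to do with how usable the data are.

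**Working it through.** The plan gives no figure for diary non-compliance or for withdrawals on that ground, so the check is mainly textual.

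**1. Does 6.3 reach diary issues?** The bullet covers significant violations as 13.3.2 defines them, and 13.3.2 names diary completion. The eligibility breach in 6.3 is introduced as an example, so it does not limit the bullet. Another 6.3 bullet builds in the investigator's judgment expressly; this one does not. Read literally, it reaches them.

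**2. Does 12.11 or 7.3.1 order withdrawal?** No. Section 12.11 uses the same label with the same cross-reference and makes exclusion optional. Section 7.3.1 presumes that the child stays on treatment.

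**3. Does any clause set precedence or exempt diaries?** None was found in 6.3, 7.3.1, 7.6, 12.11, 13.3.2 or SAP 7.

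**4. What is lost, by visit?**
- Visit 3 (Week 5): withdrawal leads to the end-of-study procedures in 8.19, which include no Sleep and Nap Diary, so Week 15 TST is never collected.
- Visit 4 (Week 15): the diary for the primary endpoint is already in hand. Only per-protocol membership is exposed.
- Visit 5 (Week 28): after the primary endpoint.

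**5. Can a child fail the Protocol rule and still have a valid Visit 3 mean TST?** Non-compliance means at most 4 complete pages in at least one week, so at most 4 + 7 = 11 of 14. The SAP needs 3 + 3 = 6 nightly TST values. TST is computed from bedtime, sleep latency, night waking and wake time; the mandatory item on hours actually slept is not used. A page can therefore be incomplete and still yield a TST value, and the valid range is 6 to 14 values. The overlap is real.

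**6. Size of the overlap (illustration only).** Assume independent nights, completion probability p per night, and a TST value only on complete pages. With X ~ Bin(7, p) per week, the share of children between the two thresholds is P(X ≥ 3)² − P(X ≥ 5)².
- p = 0.95: 1.0000² − 0.9962² = 0.0075, or 0.9 of 120
- p = 0.90: 0.9998² − 0.9743² = 0.0504, or 6.0 of 120
- p = 0.80: 0.9953² − 0.8520² = 0.2648, or 31.8 of 120

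These count children between the two thresholds. They do not count children harmed.

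**7. Power, for context.** Protocol 12.6 gives a difference of 0.72 − 0.27 = 0.45 h and a root-mean-square SD of √((0.69² + 0.45²)/2) = 0.582. A two-sided 5% t-test with 45 per group has power 0.952, which reproduces the stated 95%. Randomizing 120 to obtain 90 completers allows for 30/120 = 25% loss. If diary withdrawals took a further 5%, 10%, 20% or 30% of the 45 (assumed values), power would be about 0.94, 0.93, 0.90 or 0.86.

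**The case against.** The strongest reply is that 12.11 is the specific rule and 6.3 the general one. The same bullet of 12.11 states the discretion, the dose consequence and the label, so the label can be read as a reporting class. The structure of 6.3 supports this: it separately lists entry in breach of the protocol and prohibited medication, both already in 13.3.2, which would be redundant if the disputed bullet imported the whole list. Section 13.3.2 looks like a classification for analysis, since its categories are agreed before lock and one is compliance over the whole study. Section 7.6 treats drug non-compliance, also on that list, as something that may or may not end in withdrawal. On the SAP side, deviations are confirmed at a blinded data review meeting, and the per-protocol set serves sensitivity analyses only.

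Most of this stands as evidence of intent. A reader might infer from 6.3 that the sponsor meant to withdraw every child with a diary lapse; these passages point the other way. They exempt nothing, however, and a site that applies 6.3 as written is following the Protocol.

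A reader might also infer from step 6 that up to 32 of 120 children would lose Week 15 data. The documents do not support that. They give no completion rates, and 5-of-7 compliance is required before randomization. Reminder calls are weekly, and the electronic page prompts for starred items. Loss would also require a site to choose 6.3 over 12.11.

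**Conclusion.** Wrong as written: two rules conflict for the same event. The likely intent is 12.11, but the text does not say so.

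The consequence is limited to avoidable loss of Week 15 TST for children withdrawn at Visit 3 and avoidable loss of per-protocol membership for children kept. The number of children is unknown; steps 6 and 7 rest on assumed rates and show only how the result depends on them.

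A reader might infer bias between arms or damage to the primary analysis. Neither is supported. Sites are blinded, nothing in the documents ties diary compliance to treatment, and the mixed model on the full analysis set retains a valid Visit 3 mean TST for a child withdrawn at that visit. The per-protocol effect further depends on the blinded data review applying the withdrawal-criterion bullet literally, although SAP 7 has its own diary threshold. This is worth correcting at the next amendment.

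**What to change.** In the significant-violation bullet of Protocol 6.3, add: *except Sleep and Nap Diary non-compliance after randomization, which is handled under Section 12.11*. Leave the eligibility rule in 13.3.2 and the other 6.3 bullets unchanged.

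In SAP 7, state that diary non-compliance is judged only by the 3-of-7 diary bullet and does not count as a withdrawal criterion that was met and not acted on.

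The cost is one Protocol clause and one SAP sentence, with no new data or analysis. Because the clause changes a withdrawal criterion, it belongs in a protocol amendment with the approval that 13.3.1 requires.
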